6 INVESTIGATIONAL PLAN

6.1 Overall design

This is an open label multicenter phase I/II study. Patients will be treated with venetoclax during 14 days in combination with AZA at 75 mg/m²/day for 5 days for each cycle or 50 mg/m²/day for 5 days each cycle if relapse occurred less than 4 months after allo SCT.

Patients who meet eligibility criteria will be administered VENETOCLAX orally at starting dose in phase I part and at MTD in phase II part on days 1-14 in combination with AZA at 75 mg/m²/day for 5 days on days 1-5 for each cycle or 50 mg/m²/day for 5 days each cycle if relapse occurred less than 4 months after allo SCT.

Following cycles must be administered on day 28 or delayed until day 42 in cases of hematological toxicity. Each cycle will last 28 days starting on day 1 of each cycle when ANC > 1 G/L and platelet > 50 G/L without transfusion or when recovery of baseline level.

In the phase I part, VENETOCLAX will be given once daily orally on days 1-14 for all cycles at escalating doses starting at Dose Level 1 (defined below) in combination with AZA +/- DLI. Patients will receive at least 8 cycles of VENETOCLAX/AZA/DLI unless progression occurs. Response will be assessed after 4, 6 and 8 cycles. Patients achieving a response (see appendix 11 and 12) will be able to continue on protocol with VENETOCLAX + AZA until 12 cycles maximum then with AZA alone. In the absence of response, patients will stop treatment.

Dose Levels for Treatment in Phase I

Dose Level	VENETOCLAX (mg)	Azacitidine (mg/m ²)
-1	50 mg*	75 (50 if relapse < 4 months)
1 (Starting dose)	100 mg*	75 (50 if relapse < 4 months)
2	200 mg*	75 (50 if relapse < 4 months)
3	400 mg*	75 (50 if relapse < 4 months)

*VENETOCLAX will be given once daily orally during 14 days.

In the phase II part, VENETOCLAX will be given once daily orally on days 1-14 for all cycles at MTD defined in the phase I part of the study in combination with AZA/DLI. Patients will receive at least 8 cycles of VENETOCLAX/AZA/DLI unless progression occurs. Response will be assessed after 4, 6 and 8 cycles. Patients achieving a response (defined below) will be able to continue on protocol with VENETOCLAX + AZA until 12 cycles maximum then AZA alone. In the absence of response, patients will stop treatment.

Ramp-up** will be performed at the beginning of cycle 1:

Dose Level	VENETOCLAX D1C1	VENETOCLAX D2C1	VENETOCLAX D3C1 and beyond
-1	10 mg*	20 mg*	50 mg*
1 (Starting dose)	20 mg*	50 mg*	100 mg*
2	50 mg*	100 mg*	200 mg*

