6.6 Inclusion Criteria

Patients must meet all of the following inclusion criteria to be eligible for enrollment into the study:

1. Documented relapse of MDS or AML with marrow blasts < 30% (with WBC < 15000/mm³), after allo-SCT.
Relapse of MDS or AML is defined as:
 - ✓ Return to pretreatment bone marrow blast percentage
 - ✓ Decrement of at least 50% from maximum remission
2. Age ≥ 18 years.
3. Eastern Cooperative Oncology Group (ECOG) performance status ≤ 2.
4. Patient must have adequate organ function as indicated by the following laboratory values:

System	Laboratory Value
Renal	
Serum creatinine	< 2 mg/dl
or calculated creatinine clearance ^a	OR ≥ 30 mL/min for patients with creatinine levels > 1.5 x institutional ULN
Hepatic	
Serum total bilirubin	≤ 2.5 x ULN OR direct bilirubin ≤ ULN for patients with total bilirubin levels ≥ 2 mg/dL.
AST (SGOT) and ALT (SGPT)	≤ 2.5 x ULN
Alkaline Phosphatase	≤ 5 x ULN If > 2.5 x ULN, then liver fraction should be ≤ 2.5 x ULN
^a Creatinine clearance should be calculated per institutional standard.	

5. Patient not refractory to platelet transfusions.
6. Female subject of childbearing potential must practice at least one protocol specified method of birth control (**see appendix 3**), starting on Study Day 1 through at least 30 days after the last dose of venetoclax or 3 months after the last dose of azacitidine.
Not being of childbearing potential is defined as:
 - Age > 55 years with no menses for 12 or more months without an alternative medical cause, or
 - Age ≤ 55 years with no menses for 12 or more months without an alternative medical cause AND an FSH level > 40 IU/L, or
 - Permanent surgical sterility (bilateral oophorectomy, bilateral salpingectomy or hysterectomy).
7. Female subjects of childbearing potential must have negative results for pregnancy test performed:
 - At Screening with a serum sample obtained within 14 days prior to the first study drug administration, and
 - Prior to dosing with urine sample obtained on Cycle 1 Day 1, if it has been > 7 days since obtaining the serum pregnancy test results.

Female subjects who are not of childbearing potential at Screening do not require pregnancy testing.

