8. Male subjects sexually active with female partner(s) of childbearing potential, must agree from first dose of study drug(s) through at least 30 days after the last dose of venetoclax or 3 months after the last dose of azacitidine, whichever is later, to practice the protocol specified contraception (**see appendix 3**).
9. Patient is available for periodic blood sampling, study related assessments, and appropriate clinical management at the treating institution for the duration of the study.
10. Patient has the ability to understand and willingness to sign an informed consent form indicating the investigational nature of the study.
11. Patient is able to swallow capsules.

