13.7 Recommendations related to contraception and pregnancy

Subjects with reproductive potential are defined as sexually mature women who have not undergone a hysterectomy, bilateral oophorectomy or tubal occlusion or who have not been naturally postmenopausal (i.e., who have not menstruated at all) for at least 24 consecutive months (i.e., has had menses at any time in the preceding 24 consecutive months).

If of childbearing potential (males and females), willing to use an effective form of contraception such as latex condom, hormonal birth control, intrauterine device or double barrier method during chemotherapy treatment and for at least three months thereafter.

Pregnant women are excluded from this study. Because there is an unknown but potential risk for adverse events in nursing infants secondary to treatment of the mother with venetoclax, breastfeeding should be discontinued if the mother is treated with venetoclax.

Contact information for Safety reporting

Sponsors contact department:

[name]
Directrice du GFM
Hôpital Saint Louis
Service Hématologie Séniors
[name]
[name]
Phone : [name]
Fax : [name]
Email : [contact]

Each SAE and pregnancy must be followed up until resolution or stabilization by submission of updated reports (FU-report) to the designated recipient.

The sponsor will inform AbbVie about all serious adverse events, SUSARs and all suspected pregnancies within 24 hours of their knowledge of the event. Reports to AbbVie must be submitted via email to [contact]

The sponsor will also provide to AbbVie

- A listing of non-serious AEs, if requested
- Final study report

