24.3 Appendix 3: Contraception Recommendations

While participating in this research study, female subjects should not become pregnant or breastfeed a baby.

If female, subject must be either postmenopausal or permanently surgically sterile (refer to inclusion criteria for definitions of both) OR a female of childbearing potential, practicing at least one of the following highly effective methods of birth control, on Study Day 1 (or earlier) through at least 30 days after the last dose of venetoclax or at least 3 months after the last dose of azacitidine.

- Combined (estrogen and progestogen containing) hormonal contraception (oral, intravaginal, transdermal) associated with the inhibition of ovulation, initiated at least 1 month prior to Study Day 1.
- Progestogen-only hormonal contraception (oral, injectable, implantable) associated with inhibition of ovulation, initiated at least 1 month prior to Study Day 1.
- Bilateral tubal occlusion/ligation at least 1 month before study participation.
- Bilateral tubal occlusion via hysteroscopy (e.g., Essure®), provided a hysterosalpingogram confirms success of the procedure at least 1 month before study participation.
- Vasectomized partner(s), provided the vasectomized partner verbally confirms receipt of medical assessment of the surgical success, and is the sole sexual partner of the Female subjects of childbearing potential (trial participant).
- Intrauterine device (IUD).
- Intrauterine hormone-releasing system (IUS).
- True abstinence: Refraining from heterosexual intercourse when this is in line with the preferred and usual lifestyle of the subject (periodic abstinence [e.g., calendar, ovulation, symptothermal, post-ovulation methods] and withdrawal are not acceptable).

If required per local practices, male or female condom with or without spermicide OR cap, diaphragm or sponge with spermicide should be used in addition to one of the birth control methods listed above (excluding true abstinence).

Male subjects who are sexually active with a female of child-bearing potential, must agree to use effective contraceptive measures as defined in the protocol for female study subjects of childbearing potential from Study Day 1 through at least 30 days after the last dose of venetoclax or at least 3 months after the last dose of azacitidine, whichever is later.

Male subjects should be advised to not donate or store sperm from Study Day 1 through at least 3 months after the last dose of azacitidine.

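### Women's contraception has two alternative end dates where men's has the later of the two, and section 13.7 sets a third duration and different definitions and methods

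*Protocol*

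**What the plan says.** **End of contraception, women.** Criterion 6, in the synopsis and in section 6.6, runs from Study Day 1 "through at least 30 days after the last dose of venetoclax or 3 months after the last dose of azacitidine". Appendix 3, to which criterion 6 refers, has the same structure: "through at least 30 days after the last dose of venetoclax or at least 3 months after the last dose of azacitidine". Neither says whether one date or both must have passed.

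**End of contraception, men.** Criterion 8, again in both places, gives "30 days after the last dose of venetoclax or 3 months after the last dose of azacitidine, whichever is later". The men's paragraph of Appendix 3 has the same qualifier.

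**Treatment sequence.** Under section 6.1, responders continue on venetoclax plus azacitidine "until 12 cycles maximum then with AZA alone". No maximum number of azacitidine-alone cycles is stated.

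**Section 13.7.** This section covers the same ground in different terms. A woman has reproductive potential unless she has had certain surgery or has been naturally postmenopausal "for at least 24 consecutive months". Acceptable methods include "latex condom, hormonal birth control, intrauterine device or double barrier method", to be used during chemotherapy and for a minimum of three months afterwards. Criterion 6 instead uses "Age > 55 years with no menses for 12 or more months without an alternative medical cause", or the same 12 months plus FSH above 40 IU/L at age 55 or under. Appendix 3 requires "at least one of the following highly effective methods of birth control" and allows barrier methods only on top of one of these.

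**The concern.** Two dates joined by *or*, with nothing to say which governs, can be met by whichever comes first. The men's text shows that the protocol knows how to ask for the later date, and Appendix 3 has both versions on one page. A site comparing them could reasonably conclude that the difference is deliberate.

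The schedule makes this more than a matter of style. Venetoclax ends by cycle 12 while azacitidine may go on, so the date tied to venetoclax can pass before azacitidine has finished. Section 13.7 does not settle the matter, because it brings its own duration, definition and methods. What is at stake is participant safety and uniform application of the criteria across about 20 sites. Endpoints, sample size and error rates are not involved.

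**Working it through.** The plan states no figure to reproduce. The check is calendar arithmetic from the dosing days, followed by a comparison of the texts.

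**Inputs.** Venetoclax on days 1-14 and azacitidine on days 1-5 (section 6.1); cycle length 28 days (section 6.2). Assumptions: no cycle delays, and 3 months = 90 to 92 days.

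**Case A: both drugs stop in the same cycle** (days counted from day 1 of that cycle)
- Venetoclax date: 14 + 30 = day 44.
- Azacitidine date: 5 + 90 to 5 + 92 = days 95 to 97.
- Difference: 95 − 44 = 51 to 97 − 44 = 53 days.

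**Case B: venetoclax stops at cycle 12 and azacitidine continues alone** (study days)
- Cycle 12 day 1: 11 × 28 + 1 = 309. Last venetoclax dose: 309 + 13 = 322. Venetoclax date: 322 + 30 = 352.
- Cycle 13 day 1: 12 × 28 + 1 = 337. Azacitidine on days 337 to 341, before day 352, so still covered.
- Cycle 14 day 1: 13 × 28 + 1 = 365. Azacitidine on days 365 to 369, 13 days or more after day 352.
- On the literal reading, dosing without required contraception starts in the second azacitidine-alone cycle.
- With k azacitidine-alone cycles, the gap between the two end dates is (51 to 53) + 28k days; for k = 1 it is 79 to 81 days.

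**Comparison of the texts**

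| Item | Criterion 6 / Appendix 3 | Section 13.7 |
|---|---|---|
| End date, women | 30 days after venetoclax *or* 3 months after azacitidine | Chemotherapy period plus at least 3 months |
| Menopause | 12 months without menses; FSH > 40 IU/L also needed at age 55 or under | 24 months; no age or FSH condition |
| Surgery | Oophorectomy, salpingectomy, hysterectomy | Hysterectomy, oophorectomy, tubal occlusion |
| Tubal occlusion | A birth-control method | Ends reproductive potential |
| Condom or double barrier | Only in addition to a listed method | Listed as a method in its own right |

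The menopause definitions conflict in both directions. A woman over 55 with 18 months without menses needs no contraception under criterion 6 but has reproductive potential under section 13.7. A woman of 55 or under, naturally without menses for 24 months or more but with FSH not above 40 IU/L, is of childbearing potential under criterion 6 and outside the section 13.7 definition.

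**The case against.** The strongest reply is that criterion 6 should not be read alone. Appendix 3 opens by saying that women in the study should not become pregnant, and azacitidine alone is given on protocol. Exclusion 16 bars pregnancy over the projected study duration. The visit schedule marks a pregnancy test in the column for day 1 of cycle 2 and above. Pregnancy leads to withdrawal (section 6.8), and suspected pregnancy ends treatment (section 13.13). A reader might infer from the literal *or* that the protocol tolerates pregnancy risk during azacitidine, and these provisions contradict that. None of them, however, sets an end date for contraception, and a test detects a pregnancy without preventing it.

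Section 13.7 could close the timing gap if azacitidine alone counts as chemotherapy. The protocol does not say so, the section is headed as recommendations, and criterion 6 points to Appendix 3.

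A reader might also infer that the conflicting definitions change who is pregnancy-tested. The documents do not support this. Testing follows criterion 7 and footnote j of the visit schedule. Both use the term childbearing potential, which criterion 6 defines, and Appendix 3 refers back to the inclusion criteria for its definitions. Section 13.7 contains no testing rule. Nor does the tubal-occlusion difference change contraceptive compliance, since Appendix 3 accepts it as a sufficient method.

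Finally, the synopsis gives a treatment duration of 12 months. If that capped azacitidine, cycle 14, starting on day 365, would fall at or beyond the limit and Case B would largely disappear. It reads as a planning figure, not as a cap on azacitidine. Case A does not depend on it.

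**Conclusion.** The inconsistency is real and appears in the synopsis, section 6.6 and Appendix 3. As worded, a woman may use either of two dates that lie about 51 to 53 days apart when both drugs stop in the same cycle. If azacitidine continues alone after cycle 12, the literal rule can be met without contraception from the second azacitidine-alone cycle, but not from the first. This rests on undelayed 28-day cycles, on 3 months being 90 to 92 days, and on azacitidine alone not being limited to 12 months. Section 13.7 adds conflicts on duration, menopause, surgery and methods without clearly curing the gap.

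The likely intent is that women and men follow the same rule, which makes this a wording defect with a participant-safety consequence. The number of women affected is probably small and the protocol gives no figure. Sample size, error rates and the primary analysis are unaffected.

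**What to change.** Reconcile criteria 6 and 8 (synopsis and section 6.6), section 13.7 and Appendix 3 so that one text is in force for each of the following:
- the end of contraception for women, stating whether one or both dates must have passed and what applies during azacitidine alone;
- the definition of childbearing potential, covering menopause and sterilising surgery;
- the list of acceptable methods, including whether a barrier method is enough alone.

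Section 13.7 and the inclusion criteria with Appendix 3 should cross-refer to that single text and not restate it. Which duration, definition and method list stand is for the sponsor to decide.

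The cost is a wording amendment in those places and in any participant-facing text that repeats them. Sample size and analysis do not change. Procedures change only if the definition behind criterion 7 is altered, since that would alter who is pregnancy-tested.

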6.7 Exclusion Criteria

Patients with any one of the exclusion criteria listed below are not eligible for the study:

1. Patient has active and uncontrolled infection.
2. Patient has active acute or chronic GVHD.
3. Patient receives more than 1mg/kg/day prednisolone.
4. Patient has uncontrolled intercurrent illness or circumstances that could limit compliance with the study, including but not limited to the following: symptomatic congestive heart failure, unstable angina pectoris, uncontrolled cardiac arrhythmia, pancreatitis, or psychiatric or social conditions that may interfere with patient compliance.
5. Patient is currently participating or has participated in a study with an investigational compound or device within 30 days of initial dosing with study drug.
6. Patient has known human immunodeficiency virus (HIV) infection or HIV-related malignancy.
7. Patient has clinically active hepatitis B or hepatitis C infection.
8. Patient has a known allergy or hypersensitivity to any component of VENETOCLAX or AZA.
9. Patient with a "currently active" second malignancy, other than non-melanoma skin cancer and carcinoma in situ of the cervix, should not be enrolled. Patients are not considered to have a "currently active" malignancy if they have completed therapy for a prior malignancy, are disease free from prior malignancies for > 5 years or are considered by their physician to be at less than 30% risk of relapse.
10. Patient has received growth factors such as erythropoietin alfa (EPO) or granulocyte colony-stimulating factor (G-CSF) or has received non cytotoxic agents (including low dose oral chemotherapy) in the 30 days before inclusion. In case of previous cytotoxic treatment, an interval of 3 months is required.
11. Patient is on any systemic steroids that have not been stabilized to the equivalent of ≤ 10 mg/day prednisone during the 4 weeks prior to the start of the study drugs.
12. Patients with clinical evidence of CNS leukemia.
13. Patient has a history of GI surgery or other procedures that might interfere with the absorption or swallowing of the study drugs.

14. Subject enrolled in a Dose-Escalation cohort has received strong or moderate CYP3A inhibitors (see Appendix 2 for examples) within 3 days prior to the first dose of study drug.
15. Patient is unable to take and/or tolerate oral medications on a continuous basis.
16. Patient is pregnant or breastfeeding within the projected duration of the study.
17. Subject has a malabsorption syndrome or other condition that precludes an enteral route of administration.
18. Absence of social security.

6.8 Patient Withdrawal Criteria

Patients are free to discontinue their participation in the study at any time and without prejudice to further treatment. The Investigator must withdraw any patient from the study if that patient requests to be withdrawn. The patient's participation in this study will be discontinued due to the following reasons:

- Death
- Withdrawal of the patient's consent
- Occurrence of AEs for which permanent discontinuation of study medication is desired by the patient or considered necessary by the Investigator or by the Sponsor
- Use of illicit drugs or other substances that may, in the opinion of the Investigator, have a reasonable chance of contributing to toxicity or otherwise skewing results
- Development of an intercurrent illness or situation which would, in the judgment of the Investigator or the Sponsor, affect assessments of clinical status and study endpoints to a significant degree
- Development of a second cancer that requires treatment
- If, in the Investigator's opinion, continuation in the study would be detrimental to the patient's well-being
- Lack of patient compliance
- Serious protocol deviation that affects patient safety and accuracy and/or validity of data
- Patient is lost to follow-up
- Inability to continue in the study for any reason
- Intake of disallowed medication
 - Initiation of any experimental therapy in any period of the study until study treatment failure has been established.
 - Initiation of any anti MDS or AML therapy until study treatment failure has been established.
- Pregnancy

- Study terminated by the Sponsor

If a patient is discontinued from the study for any reason, the date of discontinuation and the reason for the discontinuation must be recorded and all evaluations specified in the EOS visit (**See the visit schedule (Appendix 1)**) must be completed. In cases of discontinuation due to an AE (including death) or pregnancy, the relevant pages of the (electronic Case Report Form) eCRF must be completed. If possible, all patients who discontinue study medication due to an AE should be followed until the medical condition returns to baseline or is considered stable or chronic.

Patients unwilling to be treated with all of the courses they are eligible for, will not be withdrawn from the study if they complete at least one treatment course, and will be followed to the full extent of the study period.

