8.7 Follow-Up

Follow-up after treatment discontinuation for all patients.

Patients will be followed at 3 months and 6 months after treatment discontinuation. Date of death or last follow-up, disease status, and ongoing hematological treatments will be collected.

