Overall survival (OS) will be defined as the number of days from the date of the first dose of study drug to the date of death. Overall survival will be analyzed by Kaplan-Meier methodology. Median OS will be calculated and 95% confidence interval for median OS will be presented. Data from subjects that are alive at the time of analysis will be censored at the date of last study visit or the last known date the subject was alive, whichever is later.

Progression-Free Survival

Progression-free survival (PFS) will be defined as the number of days from the date of the first dose of study drug to the date of earliest disease progression or death due to disease progression or febrile neutropenia. Progression-free survival will be analyzed by Kaplan-Meier methodology. Median PFS will be calculated and 95% confidence interval for median PFS will be presented. All events of disease progression will be included regardless whether the event occurred while the subject was taking the study drug or had previously discontinued the study drug. Refer to Appendix 11 and 12 for the definition of disease progression. If the subject has not experienced disease progression or death, the subject's data will be censored at the date of last disease assessment. Data for subjects without any disease assessments performed after the first dose of study drug will be censored at the time of the first dose of study drug.

Event-Free Survival

Event-free survival (EFS) will be defined as the number of days from the date of the first dose of study drug to the date of earliest disease progression or death of any cause.

Event-free survival will be analyzed by Kaplan-Meier methodology. Median EFS will be calculated and 95% confidence interval for median EFS will be presented. All events of disease progression will be included regardless whether the event occurred while the subject was taking the study drug or had previously

discontinued the study drug. If the subject has not experienced disease progression or death, the subject's data will be censored at the date of last disease assessment. Data for subjects without any disease assessments performed after the first dose of study drug will be censored at the time of the first dose of study drug.

Safety assessments

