13.13 PREMATURE TREATMENT DISCONTINUATION (Discontinuation of Individual Subjects)

Treatment will continue until the occurrence of any of the following events:

- No response after 8 cycles of therapy
- Major violation of the study protocol (violations that affect the right and safety of patients and the integrity of collected data)

- Unacceptable AE or failure to tolerate study therapy
- All grade 4 toxicities
- Persistent myelosuppression and/or cardiac toxicity
- Disease progression
- Withdrawal of consent
- Lost to follow up
- Death
- Suspected pregnancy
- Administrative decision by the investigator or the sponsor
- If the patient manifests exclusion criteria during the trial
- Subject noncompliance (deliberate protocol violations)
- A subject requires the use of a proscribed medication; the subject will need to be discontinued from treatment and end of treatment and end of study visits performed.

Where possible, patients who have discontinued their treatment prematurely will receive the same follow-up as other patients.

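### Section 6.8 ends study participation for several reasons that elsewhere only stop treatment, and names no survival or disease follow-up afterwards, in conflict with 8.7, 13.13 and 10.2

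*Protocol*

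**What the plan says.** Section 6.8 opens its list with "The patient's participation in this study will be discontinued due to the following reasons". The list includes "Occurrence of AEs for which permanent discontinuation of study medication is desired by the patient or considered necessary by the Investigator" (or the sponsor), "Lack of patient compliance", intercurrent illness, serious protocol deviation and intake of disallowed medication. The last item covers other MDS or AML therapy, but only if started before failure of study treatment is established. For a patient so discontinued, 6.8 asks for the date, the reason and the EOS evaluations. Those who stopped for an AE are also to be followed, if possible, until the event settles. Patients unwilling to take all their courses "will not be withdrawn from the study if they complete at least one treatment course"; these patients are then followed for the whole study period.

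Other sections treat the same situations differently:

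- **8.7:** "Follow-up after treatment discontinuation for all patients", with contacts at 3 and 6 months that collect death, disease status and ongoing treatments.
- **13.13:** lists unacceptable AE, non-compliance and use of a proscribed medication as reasons to stop treatment, and adds "Where possible, patients who have discontinued their treatment prematurely will receive the same follow-up as other patients".
- **10.2:** counts progression for PFS and EFS "regardless whether the event occurred while the subject was taking the study drug or had previously" stopped it. Patients without an event are censored at the last disease assessment (PFS, EFS) or at the later of last visit and last date known alive (OS).
- **Appendix 1, note c:** places the EOS visit within 30 days of stopping study drug, before either 8.7 contact.

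**The concern.** The same patient can be handled in two ways. Someone who stops venetoclax for toxicity has left the study under 6.8 but is due two further contacts under 8.7. With about 20 sites, practice may differ between them.

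What is at stake is data collection. If a site regards the patient as out of the study after the EOS visit, later deaths and progressions may never be recorded, and no analysis plan can recover them. The affected endpoints are OS, PFS, EFS and duration of response. Stopping for toxicity or intercurrent illness is plausibly related to prognosis. If it is, censoring these patients at about the time they stop is informative, and the Kaplan-Meier estimates are too favourable.

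**Working it through.** **Step 1: the texts side by side.** The protocol gives no figure to reproduce, so the first check is of wording.

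| Situation | 6.8 | 8.7 / 13.13 / 10.2 |
|---|---|---|
| Drug stopped permanently for an AE | Participation ends; EOS evaluations; AE followed if possible | Treatment ends; contacts at 3 and 6 months; later progression counts |
| Non-compliance, disallowed medication | Participation ends; EOS evaluations | Treatment ends; same follow-up where possible |
| Refuses further courses, at least one completed | Stays in the study and is followed | Followed |
| Refuses before completing one course | Not stated | Followed (8.7: all patients) |

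Death, withdrawal of consent, loss to follow-up and study termination are also in the 6.8 list. They properly end participation and are not part of the conflict.

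**Step 2: size relative to the 8.7 schedule (simulation).** Apart from the two protocol inputs marked below, all inputs are assumptions.

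- Time to stopping: exponential, median 2.8 months. This is three 28-day courses (3 × 28 = 84 days), the median in the AZA/DLI benchmark trial in section 2; treatment is capped at the protocol's 12 cycles.
- Death: exponential, median scale 6 or 9 months.
- Risk link: two equal groups, with the hazards of both stopping and death multiplied by 1.6 or 0.4.
- Censoring: stop + 6 months for everyone (8.7), against stop + 1 month for the 20% to 60% of stops handled as 6.8 withdrawals.

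| OS scale | Share of deaths observed, 8.7 | Share observed, 20% to 60% under 6.8 | Extra rise in 12-month OS |
|---|---|---|---|
| 6 months | 0.61 | 0.56 to 0.46 | about 1 to 3 points |
| 9 months | 0.48 | 0.44 to 0.35 | about 1 to 3 points |

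With the risk link removed, 12-month OS does not shift and a similar share of deaths is lost.

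**Step 3: sensitivity against complete follow-up.** A second model, also assumed, uses exponential OS with median 6 or 12 months and withdraws 10% to 30% of patients uniformly between 0.5 and 6 months. After withdrawal the hazard is multiplied by k, and patients are censored at withdrawal.

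- k = 1: no bias. For a 6-month median the true value is 0.5^(12/6) = 0.25, and the censored estimate is 0.25. Between 6% and 20% of deaths by month 12 go unobserved.
- k = 2 to 3, median 6 months: from 0.249 − 0.233 = 0.016 (10% withdrawn, k = 2) to 0.250 − 0.186 = 0.064 (30%, k = 3).
- k = 2 to 3, median 12 months: from 0.501 − 0.481 = 0.020 to 0.499 − 0.405 = 0.094.
- Over both medians with k = 2 to 3, 8% to 33% of deaths by month 12 are lost.

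These differences are larger than in step 2 partly because the comparator is complete follow-up rather than the 6-month window of 8.7. At 10% to 30% withdrawn, 3 to 9 of the 30 phase II patients are affected (30 × 0.1 to 30 × 0.3).

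**Step 4: scale.** With 30 patients and survival near 30%, the binomial standard error is √(0.3 × 0.7 / 30) = 0.084, about 8 points.

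**The case against.** The best defence is that the sections run in sequence: treatment stops, the EOS visit follows within 30 days, and the 8.7 contacts come next. On that reading EOS is in effect an end-of-treatment visit, section 8.8 gives early leavers that same visit, and 8.7 expressly covers everyone. This has force. Section 6.8 does not say that follow-up stops at EOS, nor that EOS is all that is done, so a reader who infers an explicit cut-off goes beyond the text. But 6.8 speaks of participation in the study ending, and it needs to keep certain refusers in the study so that they are followed. That suggests withdrawn patients are not followed. The two readings remain open, and sites have to choose.

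Three further limits stand:

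- Section 6.8 does not state that patients who refuse before completing one course are withdrawn. That is only the converse of what it says.
- The other-therapy item applies only before treatment failure is established, and disease progression is not in the 6.8 list. New treatment after failure is therefore not a 6.8 reason.
- 13.13 is qualified by feasibility, and 10.2 defines events rather than scheduling visits. Only 8.7 prescribes follow-up for all patients outright. The OS rule in 10.2 also uses the last date known alive and excludes no death learned of later, which softens the loss.

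**Conclusion.** The conflict is real and should be reconciled. It concerns secondary time-to-event endpoints. Its size rests on assumptions the protocol does not supply: how many stops would be handled as 6.8 withdrawals, and how strongly stopping is tied to prognosis. Under the inputs of step 2, 12-month OS rises by about 1 to 3 points beyond the 8.7 schedule, which is small beside a standard error of about 8 points. If stopping is unrelated to prognosis there is no bias, only fewer events.

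A reader might infer that the intent-to-treat analysis is broken for patients who stop in course 1. The documents do not support that: the full analysis set in 10.2 keeps all included patients whether or not they receive treatment, so such patients stay in the response denominator. The primary response rate is little exposed, because the EOS visit includes a marrow aspirate. A reader might also infer that OS and EFS are certain to be overstated; that holds only if withdrawal is linked to prognosis and sites apply 6.8 literally.

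**What to change.** Reconcile the sections by adding to 6.8 that:

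- stopping study treatment for any listed reason does not end 8.7 follow-up;
- survival and disease status are collected at 3 and 6 months after treatment stops for every treated patient, unless the patient withdraws consent to follow-up, dies, is lost to follow-up or the study is terminated;
- this applies whether or not one course was completed.

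The lists of treatment-stopping reasons in 6.8 and 13.13 can stay as they are. Moving the 6.8 reasons into 13.13 would rewrite the treatment-stopping list and is not needed.

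The cost is a wording amendment. The 3- and 6-month contacts are already planned for all patients.
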